### **3.12.** Interim Analyses

No formal interim analyses are planned for early stopping for futility or efficacy, or for the purposes of sample size reassessment.

# 4. STUDY ANALYSES

# 4.1. Patient Disposition

Patient disposition data will be tabulated and include the number enrolled, the number treated with revusiran, and the number in each patient population for analysis. The number of patients discontinuing study drug and reason for discontinuation will be summarized. The number who withdrew prior to completing the study and reason(s) for early withdrawal will be summarized.

A by-patient data listing of study completion information including the reason for premature study withdrawal or treatment discontinuation, if applicable, will be presented.

### 4.2. Demographics and Baseline Characteristics

Demographics, baseline disease characteristics, and medical history information will be summarized for the Safety Analysis Set and presented overall. No formal statistical comparisons will be performed.

Age, height, weight, and body mass index, albumin, and mBMI will be summarized using descriptive statistics (number of patients, mean, SD, median, minimum and maximum). Sex, race, and ethnicity will be summarized by presenting the numbers and percentages of patients in each category.

Baseline disease characteristics will be summarized by presenting the number and percentage of patients with or without the V30M genotype mutation. Descriptive statistics will be provided for time (years) from diagnosis with transthyretin amyloidosis (ATTR amyloidosis) to study enrollment (using date of informed consent) and time (years) from liver transplant to study enrollment. Baseline mNIS+7 score will be summarized using descriptive statistics. Karnofsky Performance Status, NYHA Classification and FAP stage at baseline will be summarized by presenting the numbers and percentages of patients in each category. The PND scores measured pre-OLT, post-OLT, and at baseline will be summarized with the number and percentage in each category. Medical history conditions will be produced for medical history conditions by SOC and preferred term. Tabular summaries will be produced for medical history conditions by SOC and preferred term. Immunosuppressant medications collected prior to the first dose of study drug will be summarized by WHO Drug anatomic therapeutic class (ATC) and preferred term.

All demographic and baseline disease characteristics data for each patient will be provided in data listings. By-patient listings for medical history, immunosuppressant medication, historical liver function values (prior to 6 months before screening) and pregnancy test results will be generated.

### 4.3. Efficacy Analysis

#### 4.3.1. Primary Efficacy Endpoint

The primary efficacy analysis will be performed after all patients have finished 6 months of treatment with study drug. The primary efficacy analysis will be based on the Evaluable Analysis Set.

The primary efficacy endpoint is the percent change from baseline in serum TTR level at 6 months. The mean percent change in serum TTR from baseline to 6 months with the associated 95% CI will be presented. A 2-sided 80% CI will also be generated. A t-test of the null hypothesis of no change in serum TTR from baseline at 6 months will be performed at the 2-sided, 0.05 confidence level.

Sensitivity analyses will be conducted to assess the robustness of the primary analysis. The sensitivity analyses will include a bootstrap 95% CI for the median percent change from baseline to 6 months in serum TTR. The bootstrap CI will be constructed using the percentile method. That is, the lower and upper limits of the bootstrap CI are defined as the 2.5th and 97.5th percentiles of the median percent change from baseline estimated from 1000 bootstrap samples. In addition to the t-test described above, a sensitivity analysis will include the p-value from the Wilcoxon signed rank test.

#### 4.3.2. Secondary Efficacy Endpoints

Analyses of secondary efficacy endpoints will be based on the Evaluable Analysis Set and Safety Analysis Set, except as noted in Section 2.1.

Descriptive statistics for actual values, change from baseline, and percent change from baseline at each scheduled visit will be provided for serum TTR. Eighty percent and 95% CIs will be produced for the mean change from baseline at Month 18. Individual serum TTR values over time will be plotted. Individual values of percent change from baseline in serum TTR will also be plotted. Plots of the mean ( $\pm$  SEM) serum TTR values and percent change in serum TTR from baseline at each scheduled visit will be generated.

Descriptive statistics will be provided for actual values, change from baseline, and percent change from baseline at each scheduled visit for the mNIS+7 composite score, and the Norfolk QOL-DN total score. Both 80% and 95% CIs will be produced for the mean change from baseline at Month 18 for these endpoints.

Components of the mNIS+7 will be summarized separately, including the NIS-Weakness, NIS-Reflexes, Nerve conduction (sum of the 5 NCS), quantitative sensory testing (QST), and postural blood pressure Similar descriptive summaries will be provided for the 5 domain scores of the Norfolk QOL-DN (see Section 6.2).

Shift tables will be created for the PND score to summarize the baseline value versus post-baseline value at each scheduled visit. An additional summary of PND score will present the shift from baseline to worst post-baseline value.

#### 4.3.3. Exploratory Endpoints

Analyses of secondary efficacy endpoints will be based on the Evaluable Analysis Set and Safety Analysis Set, except as noted in Section 2.1.

Descriptive statistics will be provided for actual values, change from baseline and percent change from baseline at each scheduled visit for continuous exploratory endpoints. For categorical values, the numbers and percentages of patients reporting each response will be generated.

For QOL questionnaires, summaries of each of the domains will also be generated.

Shift tables will be created for FAP stage to summarize the baseline value versus post-baseline value at each scheduled visit. An additional summary will present the shift from baseline to worst post-baseline value. Similar summaries will be provided for NYHA classification and KPS. For KPS, the categories will be defined as follows: 100-80 (able to carry out normal activity and to work; no special care needed), 70-50 (unable to work; able to live at home and care for most personal needs; varying amount of assistance needed) and 40-0 (unable to care for self; requires equivalent of institutional or hospital care; disease may be progressing rapidly).

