NYH	A Classification	Х	Х	 															X				Х				Х		
Karno Status	ofsky Performance	X																	Х				Х				X		
FAP S	Stage		Х																Х				Х				Х	Х	
Study Admi	Drug nistration ^g					X	X	X	X	X	Х	Х	х	X	Х	Х	Х	X	Х	Х	Х	Х	Х	Х	Х	Х	X		
mBM	I			Х															Х				Х				Х	Х	

		ening	cening ^a / eening ^a / iseline seline ^a		reening aseline	lose ^d								(A	fter D	07±1, s	tudy	W drug v	eekly vill be	Dosing admir	g nistered	l weekl	y ±2 d	ays)				q	EOS
dure	Month	Scree	Scree Base	Base	Pred		Daily	, Dosin	ıg	W1	/2	M1	4-6	M2	-11	M3	3-25	M6	7-38	6M	-51	M12	3-65	M15	7-77	M18	mination	M19	
Proce	Days/Weeks		D-42			D0	D1	D2 D3	D4	D7/	1	W3	W.	W7	W8	W12	W13	W26	W2:	W39	W4(W52	W53	W66	.9M	W78	arly Teri	W82	
	Visit Window (Days) ^c		to D -1	1	ā]	NA		±1D	±2D	±7D	±2D	±7D	±2D	±14D	±2D	±14D	±2D	±14D	±2D	±14D	±2D	±14D	±2D	±14D	E	±7D	
Prior Medic	and Concomitant cations	x	Х	х	х						•	•	•	•	•	•		X	•	•		•	•						
Adver	rse Events			L						ON	GOIN	G THI	ROU	GHOU	JT TH	e dui	RATIC	ON OF	THE	STUDY	7								
											L	abora	tory 4	Assess	ments	5													
Serun incluc	n Chemistry, ling LFTs	X X ^a X ^d X X </td х	х																		
Hema Urina	tology and lysis	X			х													x				x					X	х	
Pregn	ancy Test ⁱ	Х			Х								Х		Х	X	Х		Х		Х	X	Х		Х	X	Х	Х	
HBsA HCV	ag, HBsAb, and Ab	х																											
Coagu Asses	ulation sments ⁱ	X			х							x		x		x	Xw	x				x					Х	х	
TSH		Х																				X					Х	Х	
Antid	rug Antibodies ^k				Х							X						X				X				X	Х		
TTR I	Protein ¹		Х	Х	Х							X		X		X	$\mathbf{X}^{\mathbf{m}}$	X		Х		X	x ⁿ	Х		X	Х		
Blood term s	l samples for long- storage°		Х	х	х							x		x		x		x		Х		x		Х		X	Х		
Vitar	nin A				Х													Х				X				X	Х		
Vitam	nin B12	Х																											
Blood plasm	l samples for a PK analysis ^p				Х	X						X						X				X							

		ening	ning ^a / eline	eline ^a	lose ^d						Weekly Dosing (After D7±1, study drug will be administered weekly ±2 days)														q	EOS			
dure	Month	Scree	Scree Base	Base	Prec		Dail	y Do	osing	2	W1	/2	M1	4-6	M2	-11	M3	3-25	M6	7-38	6M	-51	M12	3-65	M15	77-77	M18	mination	M19
Proce	Days/Weeks		D-42		0	D0	D1	D2	D3	D4	D7/		W3	M.	W7	W8	W12	W13	W26	W2:	W39	W4(W52	W53	W66	.9M	W78	arly Teri	W82
	Visit Window (Days) ^c		to D -1	1	ă			NA			±1D	±2D	±7D	±2D	±7D	±2D	±14D	±2D	±14D	±2D	±14D	±2D	±14D	±2D	±14D	±2D	±14D	E	±7D
NT-pı Tropo	roBNP, BNP, and onin T and I	BNP, BNP, and I X													Х		х		х		х		х		x				

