Immu agent	mosuppressive	X											Х		X														
		L		1	L			Cardiac, Ophthalmologic, and Neurological Assessments																					
NIS ^r		Х	Х	Х															Х				Х				X	Х	
mNIS	+7 ^s		Х	Х															Х				Х				Х	Х	
Grip S	Strength Test ^s		Х	Х															Х				Х				Х	Х	
ECHO	O with Doppler ^t		Х	 															Х				Х				Χ	Х	
Ophth	nalmology Exam		Х																				Х					Х	Х
12-Le	ead ECG ^u		Х																Х				Х					Х	Х
													Qu	estio	nnaire	es							-		_			-	
Norfo	olk QOL-DN			Х															Х				Х				Х	Х	
EQ-5	D Questionnaire			X ^v															Χ				X				Х	Х	
COM Quest	PASS 31 ionnaire	ASS 31 X ^v											x				х				х	х							
Pharn Quest	armacoeconomics X											x				X				Х	х								
Colun Sever	Imbia Suicide Prity Questionnaire X												X				х				Х								

Abbreviations: aPTT=activated partial thromboplastin time; BNP=brain natriuretic peptide; COMPASS=Composite Autonomic Symptom Score; D=day; ECG=electrocardiogram; ECHO=echocardiogram; EOS=End of Study; EQ-5D= EuroQol 5 dimensions questionnaire; FAP=familial amyloidotic polyneuropathy; HBsAg=hepatitis B surface antigen;

		ening	ning ^a / eline	line ^a	lose ^d								(A	fter D	7±1, s	tudy (W lrug v	eekly] vill be	Dosinş admir	g nistered	l weekl	y ±2 d	ays)				٩_	EOS
dure	Month	Scree	Scree Base	Base	Pred		Daily	y Do	sing	M	/2	M1	4-6	M2	-11	M3	3-25	M6	7-38	6M	-51	M12	3-65	M15	7-77	M18	mination	M19
Proce	Days/Weeks		D-42			D0	D1	D2	D3	D7	*	W3	7M	W7	W8	W12	W13	W26	W27	W39	W4(W52	WS3	99M	C9M	W78	arly Teri	W82
	Visit Window (Days) ^c	to D -1		Ď			NA	.	±1D	±2D	±7D	±2D	±7D	±2D	±14D	±2D	±14D	±2D	±14D	±2D	±14D	±2D	±14D	±2D	±14D	E:	±7D	

HBsAb=hepatitis B virus antibodies; HCVAb=hepatitis C virus antibodies; HIV=human immunodeficiency virus; HP=heat pain; IEC=Independent Ethics Committee; INR=international normalized ratio; IRB=Institutional Review Board; LFT=liver function test; mBMI=modified body mass index; mNIS=Modified Neurological Impairment Score; M=month; NA=not applicable; NIS=Neurological Impairment Score; NT-proBNP=N-terminal prohormone of B-type natriuretic peptide; OLT=orthotopic liver transplant; PK=pharmacokinetic; PND=polyneuropathy disability; NYHA=New York Heart Association; PT=prothrombin time; QOL-DN=Quality of Life-Diabetic Neuropathy; QTcB=Bazett corrected QT; QTcF=Fredericia-corrected QT interval; TP=touch pressure; TSH=thyroid stimulating hormone; TTR=transthyretin; W=week; WOCBP=women of child-bearing potential.

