4.4. Withdrawal Criteria

While patients who discontinue drug are encouraged to remain in the study to complete study assessments (Section 4.3), they are free to withdraw from the study at any time and for any reason, without penalty to their continuing medical care. Patients who withdraw or have a dose reduction before 6 months of study participation may be replaced. Patients will also be withdrawn if the study is terminated.

If a patient chooses to withdraw from the study, every effort should be made to conduct the Early Termination visit. When a patient withdraws from the study, the primary reason for discontinuation must be recorded in the appropriate section of the electronic case report form (eCRF) and all efforts will be made to complete and report the observations as thoroughly as possible.

The withdrawn patient will be asked to consent to either be contacted by telephone or to allow nonpatient contact follow-up (eg, medical record check) for up to 18 months after enrolling onto the study to document their overall health status.

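### NYHA class and Karnofsky status have no Early Termination assessment in Table 1, although SAP 4.3.3 plans worst post-baseline shift tables for both

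*SAP*

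**What the plan says.** NYHA classification and KPS are exploratory endpoints in both documents (Protocol 3.4.5, SAP 1.2.5.5). SAP 4.3.3 plans shift tables for FAP stage by visit, then says: "An additional summary will present the shift from baseline to worst post-baseline value. Similar summaries will be provided for NYHA classification and KPS". SAP 4.3.2 plans the same for PND: "An additional summary of PND score will present the shift from baseline to worst post-baseline value".

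In Protocol Table 1 the NYHA and KPS rows are marked after baseline at Month 6 (Week 26), Month 12 (Week 52) and Month 18 (Week 78). Their Early Termination and End of Study cells are empty. The PND and FAP stage rows are marked at the same three visits and at Early Termination.

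Five other provisions bear on the point:
- Protocol 4.4 asks for an exit visit when a patient withdraws: "every effort should be made to conduct the Early Termination visit".
- Protocol 4.3 encourages patients who only stop study drug to stay for assessments through Month 18.
- SAP 3.11 lets unscheduled values enter categorical shift summaries.
- SAP 3.10 restricts summaries to observed data.
- SAP 3.2 gives categorical tables a missing category.

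**The concern.** A baseline-to-worst table is meant to show how far patients fell at any time on study. It can do that only if the scale is recorded when a patient leaves. For NYHA and KPS, a site that follows Table 1 at the Early Termination visit records PND and FAP stage but neither of these two ratings, and nothing else in the protocol asks for them at withdrawal.

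The gap matters because leaving may be related to the scale. Protocol 1.1.2.2 says that progression after transplant most often shows as worsening neuropathy and/or cardiac disease. Entry excludes NYHA above class 2 and requires KPS of at least 60 (Protocol 4.1 and 4.2), so there is ample room to worsen. If a patient declines after a scheduled visit and then withdraws, the worst-value table carries the earlier, better rating and the patient looks complete.

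**Working it through.** No sample-size or error-rate figure is involved. The check is a reading of Table 1, followed by simple arithmetic.

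**Step 1: where the marks fall.** Each row of Table 1 has 30 cells. Counting from 0, the header gives Month 6 = 19, Month 12 = 23, Month 18 = 27, Early Termination = 28 and End of Study = 29. The physical examination row confirms this, with marks at 19, 23, 27, 28 and 29 among others.

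| Row | Month 6 | Month 12 | Month 18 | Early Termination | Worst-value shift planned |
|---|---|---|---|---|---|
| PND | yes | yes | yes | yes | yes (SAP 4.3.2) |
| FAP stage | yes | yes | yes | yes | yes (SAP 4.3.3) |
| NYHA | yes | yes | yes | **no** | yes (SAP 4.3.3) |
| KPS | yes | yes | yes | **no** | yes (SAP 4.3.3) |

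The NYHA and KPS rows line up cell for cell with their neighbours, so the empty cells are not a displaced mark. Two of the four rating scales with a planned worst-value table have no exit value. mBMI, mNIS+7, ECHO, Norfolk QOL-DN and EQ-5D all have the Early Termination mark.

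**Step 2: who is affected.**
- *Stops drug, stays on study:* rated as scheduled to Month 18. No loss.
- *Withdraws before Week 26:* no scheduled post-baseline rating, so shown as missing under SAP 3.2. Without a Month 6 TTR result the patient is outside the Evaluable Analysis Set and appears only in the Safety Analysis Set version. The patient may also be replaced (Protocol 4.4, SAP 3.9).
- *Withdraws between Weeks 26 and 52:* the worst value is the Week 26 rating.
- *Withdraws between Weeks 52 and 78:* the worst value is the worse of the Week 26 and Week 52 ratings.
- *Withdraws with an unscheduled rating near exit:* that rating counts under SAP 3.11. No loss.

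The loss therefore sits in the third and fourth groups, and only where the patient has worsened since the last visit and has no unscheduled rating.

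**Step 3: how old the last rating can be.** Nominal gap: 52 − 26 = 26 weeks, and 78 − 52 = 26 weeks. These visits have a ±14-day (2-week) window. If the last visit was 2 weeks early, the gap is 26 + 2 = 28 weeks. If the next visit would also have been 2 weeks late, it is 28 + 2 = 30 weeks.

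**Step 4: weight of one case.** With the planned 12 patients, 1/12 = 8.3%, 2/12 = 16.7% and 3/12 = 25.0%. The documents give no expected number of withdrawals, so the range of 1 to 3 is an illustration only. Replacement or missing values would change the denominator.

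**Step 5: when the table entry is actually wrong.** NYHA must have moved by at least one class since the last visit. KPS must have crossed one of the three bands in SAP 4.3.3 (100–80, 70–50, 40–0). A fall from 70 to 60, for example, would not change the KPS table.

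**The case against.** The strongest reply is that most of the gap is already covered. Patients with no post-baseline rating are visible as missing. Patients who only stop drug are encouraged to stay. Unscheduled ratings count. The Early Termination visit still records PND, FAP stage, ECHO and a physical examination; worsening heart failure would be reportable as an adverse event, and the reason for withdrawal is recorded and summarized. In the by-visit shift tables the same patient has no value from the next visit on. All of this stands, and it limits the point to patients who leave after Month 6 having worsened since their last rating. It does not remove the point: nothing requires a rating at exit, and in the worst-value table such a patient is not shown as missing.

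It also stands that these are exploratory, descriptive tables, and that withdrawal because of decline on these scales is plausible but not shown.

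A reader might infer three stronger things that the documents do not support.
- *That the worst-value tables miss the final status of everyone who leaves.* The five groups in the working show otherwise.
- *That the Columbia suicidality scale has the same problem.* No worst-value shift is planned for it. Under SAP 4.3.3 it falls under the general rule: "For categorical values, the numbers and percentages of patients reporting each response will be generated". Its row is also displaced in the text copy of Table 1. Three evenly spaced post-baseline marks, against four in the COMPASS 31 and pharmacoeconomics rows, suggest no Early Termination mark, but this should be checked in the original table.
- *That suicidality goes unassessed at exit.* Only this scale appears not to be scheduled then. The physical examination includes a neurological/psychiatric component (Protocol 9.1.4), and adverse events are still collected.

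**Conclusion.** The point holds for NYHA and KPS as a small gap between the assessment schedule and the planned tables. Their worst-value shift tables can understate decline in patients who withdraw after Month 6, using a rating up to about 26 weeks old (up to 30 with both visit windows). Each affected patient is about 8 percentage points of a 12-patient table. How many there would be cannot be derived from the documents. The size rests on three assumptions: that the patient attends the Early Termination visit, that no unscheduled rating is taken, and that the decline crosses a class or band. The primary and secondary analyses are unaffected. For the Columbia scale the conclusion is narrower and provisional: it appears not to be scheduled at exit, and no planned worst-value table depends on it.

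**What to change.** At the next protocol amendment, mark NYHA Classification and Karnofsky Performance Status in the Early Termination column of Table 1. No SAP clause is needed, because a worst post-baseline value already covers a rating from that visit, as it does for PND and FAP stage. Check the Columbia row in the original Table 1 and, if the cell is empty, add the scale in the same amendment.

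The cost is a few minutes at a visit the protocol already asks for, with no blood draw or equipment. The amendment itself needs ethics committee and regulatory approval (Protocol 11.4), so the change should travel with other changes and does not justify an amendment of its own. It helps only for patients who attend the Early Termination visit.

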• Evaluate the effect of revusiran on various clinical activity parameters including quality of life, disease stage, modified body mass index (mBMI), and cardiac function

Methodology:

This is a multicenter, multinational, open-label study designed to evaluate the efficacy, safety, and PK of subcutaneously administered revusiran in patients with FAP with disease progression post-OLT.

Eligible, consenting patients will receive 5 daily doses of revusiran (Days 0 through 4) and a dose at Day 7, followed by once weekly doses for the duration of the study.

Visits will be held at the clinical study center for Screening, Screening/Baseline, and Baseline, and Daily Dosing (Days 0 through 4) as well as each month for the first 3 months, and approximately every 3 months through Month 18 (or Early Termination), and at the End of Study (approximately 28 days after last dose). The remaining study visits may be conducted at the clinical study center or in the patient's home.

The primary objective of the study will be evaluated by the collection of serum samples for the measurement of total TTR levels. After screening and baseline measurements, TTR will be assessed on a monthly basis for 3 months, approximately every 3 months, thereafter, and at ET.

Adverse events will be collected throughout the treatment period and at the End of Study visit.

An independent Data Monitoring Committee will be implemented for the study and will operate under a prespecified charter.

Number of Patients (planned): Approximately 12 patients will be enrolled in the study

Diagnosis and eligibility criteria:

Each patient must meet all of the following inclusion criteria to be eligible for enrollment in the study:

- 1. Male or female ≥ 18 years of age
- 2. Diagnosis of FAP with documented TTR mutation
- 3. Received an OLT \geq 12 months before the date of informed consent
- 4. An increase in polyneuropathy disability (PND) score (eg, a PND change from 1 to 2 or 3a to 3b) compared to a preliver transplant assessment OR increase in PND score between any 2 assessments postliver transplant, which in the opinion of the Investigator is due to underlying FAP progression
- 5. On stable immunosuppressive regimen with $\leq 10 \text{ mg/day}$ of prednisone for at least 3 months before the date of informed consent
- 6. Neurological impairment score (NIS) of 5 to 130 (inclusive)
- 7. Polyneuropathy Disability score of \leq 3b
- 8. Karnofsky Performance Status ≥60%

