10.2.3.2. Secondary Efficacy Endpoints

The secondary endpoints of the study are the change from baseline over 18 months for the following: serum TTR, mNIS+7, Norfolk QOL-DN, and PND score.

For continuous parameters, measurements will be summarized using descriptive statistics. Actual measurement, change, and percentage change from baseline to each scheduled visit will be summarized. To understand the effect of revusiran, the mean change from baseline at 18 months with the associated 80% and 95% CIs will also be summarized.

For categorical parameters, frequencies and percentages will be presented. To understand the effect of revusiran from baseline, the frequency and percentage of patients at each of the category shifts from baseline at 18 months will be summarized.

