#### 1.2.5.5. Exploratory Endpoints

The exploratory endpoints of the study are the assessment of change from baseline over 18 months for the following:

- mBMI;
- FAP stage;
- Grip strength;
- New York Heart Association (NYHA) classification;
- Karnofsky Performance Status (KPS);
- Echocardiogram parameters;
- Cardiac biomarkers;
- EuroQoL questionnaire in 5-dimensions;
- Composite Autonomic Symptom Score (COMPASS) 31 questionnaire;
- Columbia Suicide Severity Rating Scale questionnaire;
- Pharmacoeconomics questionnaire;
- Optional exploratory residual liver tissue evaluation.

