## 6.4. Familial Amyloidotic Polyneuropathy (FAP) Stage

### 6.5. New York Heart Association (NYHA) Classification of Heart Failure

Class	Symptomology	
Ι	No symptoms. Ordinary physical activity such as walking and climbing stairs does not cause fatigue or dyspnea.	
Π	Symptoms with ordinary physical activity. Walking or climbing stairs rapidly, walking uphill, walking or stair climbing after meals, in cold weather, in wind, or when under emotional stress causes undue fatigue or dyspnea.	
Ш	Symptoms with less than ordinary physical activity. Walking 1 to 2 blocks on the level and climbing more than 1 flight of stairs in normal conditions causes undue fatigue or dyspnea.	
IV	Symptoms at rest. Inability to carry on any physical activity without fatigue or dyspnea.	

	100	Normal no complaints; no evidence of disease
Able to carry on normal activity and to work; no special care needed.	90	Able to carry on normal activity; minor signs or symptoms of disease
	80	Normal activity with effort; some signs or symptoms of disease
Unable to work; able to live at	70	Cares for self; unable to carry on normal activity or to do active work
home and care for most personal needs; varying amount of assistance needed.	60	Requires occasional assistance, but is able to care for most of his personal needs
	50	Requires considerable assistance and frequent medical care
	40	Disabled; requires special care and assistance
Unable to care for self; requires equivalent of institutional or hospital care; disease may be progressing rapidly.	30	Severely disabled; hospital admission is indicated although death is not imminent
	20	Very sick; hospital admission necessary; active supportive treatment necessary
progressing rupidity.	10	Moribund; fatal processes progressing rapidly
	0	Dead

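### The three-band Karnofsky shift tables cannot show most 10-point changes, and no other planned summary clearly shows within-patient change

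*SAP*

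**What the plan says.** KPS is an exploratory endpoint, defined in both documents as change from baseline over 18 months (Protocol Section 3.4.5; SAP Section 1.2.5.5). SAP Section 4.3.3 describes shift tables for FAP stage, at each scheduled visit and from baseline to worst later value, and then extends them: "Similar summaries will be provided for NYHA classification and KPS". For KPS alone it defines grouped categories. The passage opens with "For KPS, the categories will be defined as follows: 100-80"; the other two bands run from 70 down to 50 and from 40 down to 0. The bands are the three group headings printed beside the scale in Protocol Appendix 16.5 and SAP Section 6.6.

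The scale itself has 11 levels in steps of 10, each with its own description; level 90, for example, reads "Able to carry on normal activity; minor signs or symptoms of disease". Inclusion criterion 8 sets the entry floor: "Karnofsky Performance Status ≥60" percent.

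For categorical secondary endpoints, Protocol Section 10.2.3.2 says that "the frequency and percentage of patients at each of the category shifts from baseline at 18 months will be summarized". Section 10.2.3.3 carries this over to the exploratory endpoints in general terms. Neither section defines KPS categories.

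**The concern.** A shift table shows a change only if the patient crosses a band edge. With entry at 60 or above, only two edges matter: between 80 and 70, and between 50 and 40. A patient who goes from 70 (looks after himself or herself) to 50 (needs a good deal of help and regular medical attention) is tabulated as unchanged, although 50 is below the trial's own entry floor. A patient who goes from 80 to 70 is tabulated as shifted. The worst-value table uses the same bands, so it cannot recover what the by-visit table misses.

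The study is single-arm, plans about 12 patients, and enrols people whose neuropathy has progressed. Within-patient change is the only descriptive evidence that KPS can offer. If the tables are insensitive to changes of one or two levels, the endpoint as tabulated says little about change over 18 months, for better or worse.

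**Working it through.** The documents state no power, precision or expected-change figure for KPS, so there is no plan figure to reproduce. The check is a direct enumeration.

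**Inputs.** Baseline levels b = 60, 70, 80, 90, 100 (inclusion criterion 8 and the 10-point scale). Bands: A = 100-80, B = 70-50, C = 40-0 (SAP Section 4.3.3).

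**Rule.** A change of d points is hidden when band(b − d) = band(b) for a fall, or band(b + d) = band(b) for a gain.

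| Baseline | Fall of 10 | Fall of 20 | Fall of 30 |
|---|---|---|---|
| 100 (A) | 90, A: hidden | 80, A: hidden | 70, B: shown |
| 90 (A) | 80, A: hidden | 70, B: shown | 60, B: shown |
| 80 (A) | 70, B: shown | 60, B: shown | 50, B: shown |
| 70 (B) | 60, B: hidden | 50, B: hidden | 40, C: shown |
| 60 (B) | 50, B: hidden | 40, C: shown | 30, C: shown |
| Hidden | 4 of 5 | 2 of 5 | 0 of 5 |

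**Gains of 10** (possible from 60 to 90): 60 to 70, 80 to 90 and 90 to 100 are hidden; only 70 to 80 shows. Hidden: 3 of 4.

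**Gains of 20** (possible from 60 to 80): 60 to 80 and 70 to 90 show; 80 to 100 is hidden. Hidden: 1 of 3.

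**All possible falls.** A baseline b has b/10 lower levels, so there are 6 + 7 + 8 + 9 + 10 = 40 baseline-to-lower pairs. Six are hidden: 100 to 90, 100 to 80, 90 to 80, 70 to 60, 70 to 50 and 60 to 50. The loss is confined to falls of 10 and 20 points.

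**Does another planned summary show the change?**
- SAP Section 4.3.3 gives change-from-baseline statistics for continuous exploratory endpoints. It handles KPS through categories, as does the baseline summary in Section 4.2, and nowhere says that KPS will be summarised as a 10-point score.
- The same section plans counts of each response for categorical values. It does not say whether these use the 10-point levels for KPS. In either case they are marginal counts at a visit, not change within a patient.
- Listings (SAP Section 3.10; Protocol Section 10.2) will hold every recorded value. The reader would have to assemble the changes by hand.
- The table shells in SAP Section 7.4 appear only as a heading in the text available, so the intended layout cannot be checked.

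**With 10-point levels.** Every change of 10 points or more moves to a different category, so the hidden counts become 0 of 5 for falls of 10 and 0 of 5 for falls of 20.

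**The case against.** The bands are not an arbitrary collapse. They are the scale's own functional groups: able to work; unable to work but living at home; unable to care for oneself. They were fixed in advance. Going from 80 to 70 crosses a functional boundary and going from 70 to 50 does not, so the table answers a legitimate question, and any grouping gives some discordance at its edges. KPS is one exploratory measure among many, with no hypothesis test. Progression is also followed by mNIS+7, Norfolk QOL-DN, and PND, FAP stage and NYHA shifts. With about 12 patients and post-baseline KPS at Months 6, 12 and 18, a listing is short enough to read. All of this stands, and it keeps the point small. It does not supply a summary of within-patient change at the resolution at which the scale is recorded.

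A reader might infer three stronger things that the documents do not support:

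- **That the SAP departs from the protocol.** Protocol Section 10.2.3.2 asks for category shifts but does not name KPS, and no section requires shifts on all 11 levels.
- **That the tables are tilted towards apparent stability.** Resolution is lost for gains as well as falls, and nothing in either document rests a claim of stabilisation on the KPS bands.
- **That four in five patients with a 10-point fall would be missed.** The fraction is over baseline levels. The share of patients depends on a baseline distribution that is not given: it would be none if everyone entered at 80 and all if no one did.

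**Conclusion.** The point holds as a minor weakness of reporting. From the permitted entry levels, the banded tables show no shift for 4 of 5 ten-point falls, 2 of 5 twenty-point falls and 3 of 4 ten-point gains; every fall of 30 points or more from those levels is shown. The result rests only on the entry criterion and the band limits. How many patients it would affect cannot be computed from the documents. The primary TTR analysis is untouched. This is a worthwhile improvement to one exploratory endpoint, not a defect that threatens a conclusion.

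**What to change.** In SAP Section 4.3.3, build the KPS shift tables on the recorded 10-point levels, by visit and to worst post-baseline value. At the least, add the number and percentage of patients with a change of 10 or more and of 20 or more points, in each direction at each scheduled visit, and with falls of those sizes at the worst post-baseline value. Keep the three-band table as a supplement, because its functional groups are easy to interpret.

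No new data are needed. The cost is one more table. A full-level table has at most 5 baseline rows by 11 outcome columns (55 cells), which will be sparse with about 12 patients; the counts of changes are the compact alternative.
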